- c. ALT or AST >3x ULN and total bilirubin >2x ULN or INR >1.5

Patients with life threatening, grade 3 non-hematologic toxicity regardless of relationship to study drug should discontinue study treatment permanently. Examples include myocardial infarction or stroke.

In the event of other Grade 3 treatment-related toxicity at the time of a scheduled treatment day, the dose will be held and subjects will be assessed at least weekly. If recovery to \leq Grade 1 delays the next dose by only one week, treatment may resume then without dose reduction. If recovery to \leq Grade 1 delays the next dose by 2 or 3 weeks, treatment must be resumed at a reduced dose (Table 7). If treatment on day 8 of a cycle is held, the dose should be skipped and treatment resumed with day 1 of the following cycle. If treatment on day 1 is delayed, the entire cycle should be delayed, maintaining the same cycle number. The use of prophylactic G-CSF in subsequent cycles is recommended to prevent recurrence of neutropenia that would require a dose reduction. If recovery to \leq Grade 1 requires more than a three-week delay, treatment must be permanently discontinued.

After **cycle 1 day 1** treatment initiation should be withheld until ANC is $> 1000 / \mu\text{L}$. If day 8 is held for ANC $< 1000 / \mu\text{L}$, that dose will be missed. Resume dosing with next cycle. If delay more than 4 weeks, discontinue treatment. GCSF prophylaxis prior to cycle 2 is recommended if clinically appropriate.

For grade ≥ 3 neutropenia (ANC $< 1000 / \mu\text{L}$) after cycle 1 day 1 or after day 1 of subsequent cycles, hold day 8, initiate growth factor support and administer prophylactic growth factors with each subsequent cycle. Resume dosing with the next cycle only if toxicity resolves. **In subsequent treatment cycles**, treatment initiation for Day 1 of the cycle should be withheld until ANC $> 1000 / \mu\text{L}$ and GROWTH FACTORS should be used as clinically indicated. Patient will be assessed weekly for grade 3 ANC (ANC $< 1000 / \mu\text{L}$ to $500 / \mu\text{L}$) and bi-weekly for grade 4 ANC (ANC $< 500 / \mu\text{L}$). If delay more than 3 weeks, discontinue. Resume dosing at the next cycle if toxicity recovers to \leq grade 2 within 3 weeks. All subsequent cycles should be administered with growth factor support.

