In the event of neutropenia **grade ≥ 3** at the time of scheduled treatment day **despite growth factor prophylaxis**, resume treatment if the toxicity recovers to \leq grade 2 within 2 or 3 weeks with a 25% dose reduction for the first event (7.5mg/kg for a starting dose

of 10mg/kg). For subjects whose starting dose was 10mg/kg there will be a 50% dose reduction (5 mg/kg) for the second event that occurs while the patient is receiving prophylactic growth factors. Subjects will discontinue treatment for the 3rd occurrence while on growth factor support. NO DOSE REDUCTION IS REQUIRED IF TOXICITY RESOLVES WITHIN 1 WEEK.

Table 7. Dose Reduction Requirements for Severe Treatment-Related Toxicity

Event	Occurrence	Study Drug Dose
Grade 4 hematologic toxicity \geq 7 days OR Grade 3 febrile neutropenia (ANC < 1000/mm ³ , fever \geq 38.5°C), OR Grade 3 thrombocytopenia with clinically relevant bleeding OR Grade 4 thrombocytopenia, regardless of duration OR Any Grade 3 nausea, vomiting or diarrhea due to treatment, or other Grade 3 non-hematologic toxicity persisting $>$ 48 hours despite optimal medical management. OR At time of scheduled treatment, Grade 3 hematologic or Grade 3 non- hematologic toxicity which delays dose by 2 or 3 weeks for recovery to \leq Grade 2 or baseline.	First	7.5 mg/kg
	Second	5 mg/kg
	Third	Study drug will be discontinued
Hematologic toxicity: \leq Grade 1 (ANC \geq 1500/mm ³ or baseline level, Platelets \geq 75,000/mm ³ , or Hgb \geq 10.0 g/dL or baseline level); Grade 2 (ANC $>$ 1000/mm ³ , Platelets $>$ 50,000/mm ³ , or Hgb \geq 8 g/dL); Grade 3 (ANC < 1000/mm ³ , Platelets < 50,000/mm ³ , or Hgb < 8.0 g/dL); Grade 4 (ANC < 500/mm ³ , Platelets < 25,000/mm ³ , or Hgb < 6.5 g/dL).		
Note: In the event of adverse effects unrelated to study drug administration (both hematological and non- hematological adverse events), decision to dose delay or dose reduce is investigator discretion, based on the tolerability of the toxicities.		

The development of any of the severe toxicities noted in table 7 due to treatment requires permanent dose reduction for that subject by 25% of the assigned dose for first occurrence, 50% of the initial assigned dose for second occurrence. Subjects whose starting dose was 10mg/kg will discontinue treatment entirely in the event of a third occurrence (Table 7).

Do not re-escalate the Sacituzumab Govitecan dose after a dose reduction for toxicity has been made.

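### Section 6.4.1 measures the same 2–3 week dose delay to Grade 1 in the text and to Grade 2 or baseline in Table 7, so the dose-reduction trigger differs

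*Combined protocol and SAP*

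**What the plan says.** The relevant paragraph of section 6.4.1 opens: "In the event of other Grade 3 treatment-related toxicity at the time of a scheduled treatment day, the dose will be held". It then makes three decisions depend on recovery to Grade 1 or lower. A one-week delay means resuming at the same dose. For a longer delay, if recovery to no worse than "Grade 1 delays the next dose by 2 or 3 weeks, treatment must be resumed at a reduced dose (Table 7". Finally, if recovery to no worse than "Grade 1 requires more than a three-week delay, treatment must be permanently discontinued".

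Table 7 is titled "Dose Reduction Requirements for Severe Treatment-Related Toxicity". Its last trigger is Grade 3 hematologic or non-hematologic "toxicity which delays dose by 2 or 3 weeks for recovery to \leq Grade 2 or baseline". The dose column gives 7.5 mg/kg at the first occurrence, 5 mg/kg at the second, and discontinuation at the third. The text below the table says that any listed toxicity "requires permanent dose reduction for that subject by 25% of the assigned dose for first occurrence", and adds: "Do not re-escalate the Sacituzumab Govitecan dose after a dose reduction for toxicity has been made".

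Neutropenia has its own paragraphs in 6.4.1. One lets dosing resume at the next cycle on recovery to no worse than "grade 2 within 3 weeks. All subsequent cycles should be administered with growth factor support". Another, for neutropenia despite growth factor prophylaxis, also uses Grade 2. Both agree with the Table 7 row.

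**The concern.** The paragraph sends the reader to Table 7 for the reduced dose, and the table describes the same event and the same delay, but the two count the delay to different recovery levels. In a multicenter trial, one site may work from the paragraph and another from the table, and the same course of toxicity can then lead to a different dose.

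The choice matters to the patient because it cannot be undone. A reduction is permanent, and each counted occurrence moves the patient one step closer to 5 mg/kg and then to discontinuation.

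**Working it through.** No plan figure is at issue, so the check is a comparison of the two rules.

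| | Paragraph in 6.4.1 | Table 7 delay row |
|---|---|---|
| Event | Other Grade 3 treatment-related toxicity on a dosing day | Grade 3 hematologic or non-hematologic toxicity on a dosing day |
| Recovery level | Grade 1 or lower | Grade 2 or lower, or baseline |
| One-week delay | Resume, same dose | Not a trigger |
| Delay of 2 or 3 weeks | Resume at reduced dose | 7.5 mg/kg, then 5 mg/kg, then stop |
| Delay over 3 weeks | Permanent discontinuation | Silent |

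**Width of the gap, from the Table 7 footnote.**
- Platelets: 75,000/mm³ or more for Grade 1, above 50,000/mm³ for Grade 2. Gap: 75,000 − 50,000 = 25,000/mm³. Entry requires at least 100,000/µl (section 3.1.10), so a baseline allowance would not narrow it.
- Hemoglobin: 10.0 g/dL or baseline for Grade 1, 8 g/dL for Grade 2. Gap: at most 10 − 8 = 2 g/dL. For a patient enrolled at the 9 g/dL minimum, it is 9 − 8 = 1 g/dL, because the footnote accepts baseline.

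**Case A, the reduction trigger.** Take a held Day 1 dose, since a held Day 8 dose is simply skipped. Platelets are Grade 3 (below 50,000/mm³) without bleeding on the dosing day, between 50,000 and 75,000/mm³ at week 1, and at least 75,000/mm³ at week 2.
- Paragraph: the dose is held until week 2. The delay is two weeks, so the dose must fall to 10 × 0.75 = 7.5 mg/kg.
- Table 7 row: Grade 2 was reached at week 1. The delay to that level is one week, so the row is not met. No other Table 7 trigger applies.

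Anemia moving between the same grades gives the same result.

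**Case B, stopping.** Toxicity reaches Grade 2 at week 2 or 3 and is still Grade 2 after week 3.
- Paragraph: permanent discontinuation.
- Table 7 row: the wording suggests that recovery has been reached and that treatment goes on at 7.5 mg/kg (first occurrence) or 10 × 0.50 = 5 mg/kg (second). The table does not itself order resumption, so this is an inference.

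**Case C, neutropenia.** The paragraph speaks of other toxicity, and the dedicated paragraphs suggest that neutropenia is outside it. Yet it also recommends prophylactic G-CSF to prevent recurrent neutropenia, which suggests the opposite. If neutropenia is inside, the paragraph requires an ANC of at least 1500/mm³ or baseline, while the neutropenia paragraphs accept Grade 2 (above 1000/mm³).

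**The case against.** The strongest reply is that the paragraph is the operative rule. It alone says when to hold, resume and stop, and its reference to Table 7 can be read as pointing only to the dose column. Table 7 lists reduction triggers and, apart from the third occurrence, has no stopping rule. A site that follows the paragraph throughout breaks no line of the table. This stands, and it limits the risk to sites that work from the table. It does not remove the mismatch, because the table states its own recovery level for the same delay.

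The second reply is that the reach is narrow. Table 7 already reduces the dose for any Grade 3 nausea, vomiting or diarrhea due to treatment, for other Grade 3 non-hematologic toxicity lasting beyond 48 hours despite optimal management, for Grade 3 thrombocytopenia with relevant bleeding, for all Grade 4 thrombocytopenia, and for Grade 4 hematologic toxicity of 7 days or more. This stands too. A reader might infer that the reduction trigger is in conflict across all Grade 3 toxicity; the other rows settle most non-hematologic cases whichever recovery level is used.

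Third, section 5.8 separately lists a treatment delay beyond 3 weeks as a reason for removal. That supports the time limit but does not say which grade permits re-dosing, so it leaves Case B open.

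Finally, nothing in the documents proves that Grade 1 was the intended level. The Cycle 1 Day 1 rule in 6.4.1 uses Grade 1 or baseline with a three-week limit; Table 7 and the neutropenia paragraphs use Grade 2. The choice belongs to the sponsor-investigator.

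**Conclusion.** The inconsistency is real and should be corrected. It directly affects the dose-reduction trigger, mainly for anemia or non-bleeding thrombocytopenia with the recovery timing of Case A. The conflict over stopping (Case B) is implied only. The conflict over neutropenia (Case C) depends on whether the paragraph covers it, which the text does not settle.

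The number of patients affected cannot be estimated and may be small. A reader might take the anemia row of Table 2 (13 of 327 at 10 mg/kg, 4.0%) as its size. That row counts treatment interruptions for anemia without giving the grade or the time to recovery, so it measures a different group. A reader might also infer damage to the efficacy conclusions. The documents do not support that: the primary analysis, sample size and power do not use these thresholds.

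**What to change.** Use one recovery grade per toxicity type in both places.

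- In the paragraph: state that it applies to Grade 3 treatment-related toxicity other than neutropenia, which follows the neutropenia paragraphs (Grade 2 or lower), and change the threshold for all three decisions to Grade 1 or lower, or baseline level.
- In the Table 7 delay row: change the recovery level to Grade 1 or lower, or baseline, with Grade 2 or lower for neutropenia.

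The carve-out in the paragraph is needed. Without it, a paragraph read as covering neutropenia would still contradict the neutropenia rules after the table is corrected. Adding baseline to the paragraph matters mainly for non-hematologic toxicity, since the footnote already allows it for ANC and hemoglobin.

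If the sponsor-investigator confirms that Grade 2 was intended for all toxicities, change all three thresholds in the paragraph to Grade 2 or lower, or baseline, and leave the Table 7 row as it is.

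The cost is a short amendment to one paragraph and one table row, plus a site memo. Under the first option, patients with Grade 2 toxicity above baseline that lasts past 3 weeks stop treatment, as the paragraph already requires.

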The dose guidelines will be followed with a goal of being able to give the first cycle without requiring dose reduction, delay, or discontinuation or cytokine support at the time the second cycle is given.

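### Section 6.4.1 gives instructions of different strength on growth factor prophylaxis after Grade 3 or higher neutropenia in cycle 1, and does not say which governs

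*Combined protocol and SAP*

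**What the plan says.** Three consecutive parts of Section 6.4.1 matter.

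**Paragraph A** concerns the period after cycle 1 day 1. It opens the relevant case with "If day 8 is held for ANC" below 1000/µL. The dose is then missed and dosing resumes with the next cycle. It closes with "GCSF prophylaxis prior to cycle 2 is recommended if clinically appropriate".

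**Paragraph B** follows directly. It addresses Grade 3 or higher neutropenia, which it identifies as ANC below 1000/µL, "after cycle 1 day 1 or after day 1 of subsequent cycles, hold day 8, initiate growth factor support". It continues with the instruction to "administer prophylactic growth factors with each subsequent cycle". Later, under a lead-in about subsequent treatment cycles, it says "GROWTH FACTORS should be used as clinically indicated". It ends with "All subsequent cycles should be administered with growth factor support".

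**The dose steps** come next. For Grade 3 or higher neutropenia on a scheduled treatment day despite growth factor prophylaxis, with recovery in 2 or 3 weeks, the first event brings a 25% reduction. A second event while on prophylactic growth factors brings a 50% reduction, and a third while on growth factor support ends treatment.

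**The concern.** A safety instruction for one of the drug's most common severe toxicities should give one answer for one patient. Here the answer depends on the sentence a site reads. The trial is multicenter (Section 5), so different readings can coexist.

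Two things are at stake. The first is protection: two men with the same count on the same day can enter cycle 2 with and without prophylaxis, each with support in the text. The second is dosing: the steps above are worded to count neutropenia that occurs despite, or during, prophylaxis. Whether a later event counts can therefore depend on which sentence was followed earlier. Section 8.4.2 plans toxicity rates with 95% confidence intervals, and part of any difference in neutropenia or dose intensity could then reflect how sites read the text.

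**Working it through.** The plan states no figure on this point, so the check is a comparison of text.

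**Step 1: do the triggers coincide?** Paragraph A is triggered by a day 8 dose held for ANC below 1000/µL. Paragraph B is triggered by Grade 3 or higher neutropenia after day 1, including cycle 1 day 1, with day 8 held. Paragraph B itself equates that grade with ANC below 1000/µL, and the note under Table 7 defines Grade 3 the same way. For cycle 1 the two triggers are one event. As an illustration, a man with ANC 800/µL on cycle 1 day 8 meets both.

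**Step 2: do the instructions agree for that man?**

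| Place in 6.4.1 | Period covered | Instruction | Strength |
|---|---|---|---|
| Paragraph A, last sentence | Before cycle 2 | "GCSF prophylaxis prior to cycle 2 is recommended if clinically appropriate" | Recommended, with judgement |
| Paragraph B, first sentence | Each later cycle | "administer prophylactic growth factors with each subsequent cycle" | Directed |
| Paragraph B, middle | Later cycles | "GROWTH FACTORS should be used as clinically indicated" | Judgement |
| Paragraph B, last sentence | All later cycles | "All subsequent cycles should be administered with growth factor support" | Directed |

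The paragraph before A, on other Grade 3 treatment-related toxicity, adds a further variant: prophylactic G-CSF in later cycles is recommended.

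**Step 3: is precedence stated anywhere?** Section 6.4, the rest of Section 6.4.1, Table 7 and Appendix B do not say which sentence governs.

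**Step 4: does it reach the dose?** The neutropenia steps take a 10 mg/kg starting dose to 10 × 0.75 = 7.5 mg/kg, then 10 × 0.50 = 5 mg/kg, then to discontinuation. Suppose two men have the same Grade 3 count on a later day 1, each recovering in 2 weeks. If one was on prophylaxis, the first step applies to him as worded. If the other was not, that paragraph does not describe him. Paragraph B, which does, allows dosing to resume after recovery to Grade 2 or lower within 3 weeks and mentions no reduction.

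**Step 5: can the number affected be sized?** Table 3 (Section 1.3) gives 75 / 420 = 17.9% with Grade 3 or higher neutropenia. It has no restriction to cycle 1 or day 8. By Table 2 in the same section, a total of 420 pools 81 + 327 + 9 + 3 patients at 8, 10, 12 and 18 mg/kg. At 10 mg/kg, Table 2 shows neutropenia leading to treatment interruption in 61 / 327 = 18.7%, again without a cycle. No input gives the rate of day 8 holds in cycle 1.

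**The case against.** **A harmonizing reading exists.** Paragraph A's last sentence can be taken as general advice before cycle 2, with paragraph B as the specific rule. The sentence on clinical indication in B can be taken as addressed to all patients on day 1 of later cycles, in line with the general allowance in Section 6.4. This is a fair reading, but no text establishes it, and A's sentence closes a passage about a day 8 dose held for the same ANC threshold.

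**The instructions are not mutually exclusive.** A site that gives growth factor with every later cycle complies with both paragraphs. That is true. The conflict arises for a site that uses the discretion in A and so departs from B. Neither paragraph uses the word required, and A does recommend prophylaxis. The text shows that sites can differ, not that they will.

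**Table 7 softens the dose consequence.** Its last criterion, Grade 3 hematologic toxicity delaying a scheduled dose by 2 or 3 weeks, carries no condition on prophylaxis. A site working from Table 7 would reduce the dose for both men in Step 4. This stands as a limit: the dose paths diverge only where the neutropenia paragraph is taken as governing. It also shows that the dose steps need the same reconciliation.

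**Other passages might seem to conflict too.** A reader might set the growth factor requirement at cycle 1 for patients aged 65 or over (Section 6.4), or the closing goal of giving the first cycle "without requiring dose reduction, delay, or discontinuation or cytokine support at the time the second cycle is given", against these paragraphs. Neither contradicts them. The age rule concerns cycle 1 and a different trigger. The closing sentence states a goal, and a man with Grade 3 neutropenia who needs support has missed it without any rule being broken.

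**Conclusion.** The text is wrong as written: an internal inconsistency in a safety instruction. For ANC below 1000/µL after cycle 1 day 1 with day 8 held, Section 6.4.1 both leaves prophylaxis from cycle 2 to judgement and directs it. The second paragraph is mixed within itself, so the ambiguity there extends to later cycles. The conclusion rests on the two triggers being the same event, which the protocol's own Grade 3 definition supports, and on the absence of any statement of precedence. The effect on dose path is possible, not certain, given Table 7.

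The number of affected men is unknown. A reader might multiply Table 3 by the enrolment target: 0.179 × 55 = 9.8 men, or, adding the separate term for decreased neutrophil count without overlap, (75 + 41) / 420 = 27.6% and 0.276 × 55 = 15.2 men. The documents do not support this as a count for the case. The rates cover any cycle and several doses, the two terms may overlap, and this trial requires growth factor at cycle 1 in men aged 65 or over.

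A reader might also infer damage to the primary endpoints. Nothing in the documents shows it, and in a single-arm trial there is no between-arm bias. The sponsor should correct the wording, but the primary analyses do not depend on it.

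**What to change.** Reconcile the growth factor sentences in the two paragraphs of Section 6.4.1 into one rule. State whether growth factor after a first Grade 3 or higher neutropenia is directed or discretionary, and use the same wording each time it appears. Then align the dose steps that depend on prophylaxis, and the matching criterion in Table 7, so that it is clear which events count. Which rule stands is for the sponsor's clinicians to decide.

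The same two paragraphs also differ on the delay that ends treatment (more than 4 weeks against more than 3 weeks). That is a separate point, but it can be reconciled in the same edit.

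The cost is a wording change in the next amendment. The sample size and the analyses do not change.

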6.4 Dose modification of Sacituzumab Govitecan

The current established dose schedule for Sacituzumab Govitecan is 10 mg/kg on days 1 and 8 repeated every 21 days given as an intravenous infusion at the rates described in Section 6.3.3. There should be a minimum of 14 days between the day 8 infusion and the day 1 infusion of the next cycle in the absence of progression of disease or unacceptable toxicity. Planned deviations in treatment schedule are allowable up to 7 days due to holidays, vacations or personal reasons. The protocol allows aggressive medical management of patients in order to avoid dose reduction and dose delay as much as possible. Growth factors should be initiated once the ANC starts decreasing and may be used prophylactically as clinically indicated. In patients who would be considered high risk for neutropenia (those who experienced febrile neutropenia or Grade 3-4 neutropenia with prior treatments), use of growth factors should be initiated early on and used prophylactically as early as Cycle 1. Growth factors are required at cycle 1 for all patients \geq 65 years old.

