6.4.1 Dose reduction and termination guidelines

The most likely toxicities of Sacituzumab Govitecan are expected to be gastrointestinal symptoms and hematologic suppression. All subjects are closely monitored over the course of their treatment. NCI CTCAE v4.0 is used to grade all AEs and to provide the following dose reduction, delay or cessation guidelines in the event of treatment-related toxicity.

In this phase II study, subjects will receive 10 mg/kg Sacituzumab Govitecan once weekly for 2 consecutive weeks followed by 1 week rest in cycles of 21 days, with treatment continued in the absence of progression or unacceptable toxicity. Neutropenia, GI toxicity, fatigue and alopecia were the most common toxicities in phase I testing. All subjects will be closely monitored over the course of their treatment, with NCI CTCAE v4.0 used to grade all AEs and to provide dose reduction, delay or cessation guidelines in the event of toxicity.

On the first treatment day (Cycle 1 Day 1), if a subject experiences ANC $<1000/\mu\text{l}$ or \geq Grade 2 GI toxicity (disease related or from prior treatments), treatment initiation should be withheld until resolved to \leq Grade 1 or baseline level. It is recommended that growth factor support prophylaxis be administered to subjects who receive treatment and whose Cycle 1 Day 1 ANC is $<1500/\mu\text{l}$ and $\geq 1000/\mu\text{l}$.

If recovery to \leq Grade 1 or baseline level requires more than three-week delay, the subject should be withdrawn from the study.

Treatment will be permanently discontinued for a subject in the event of any \geq Grade 3 infusion reactions or for any Grade 2 immediate-type allergic/hypersensitivity infusion reactions (e.g., generalized urticaria, wheezing, hypoxia, dyspnea), which occur after pre-medication with antihistamines, H2 blockers and steroids.

Patients with grade 4 non-hematologic toxicity deemed at least possibly related must permanently discontinue the study drug except for the following situations:

- a. Chloride, bicarbonate, magnesium, phosphate or glucose abnormalities that last <72 hours, if not clinically complicated, and resolve spontaneously or respond to conventional medical interventions
- b. Amylase or lipase elevations that are not associated with symptoms or clinical manifestations of pancreatitis.

Treatment should be permanently discontinued if:

- a. ALT or AST >8x ULN
- b. ALT or AST >5x ULN for more than 2 weeks

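### Section 6.4.1 counts neutropenia events in two conflicting ways, so one event can call for 7.5 or 5 mg/kg and the next for 5 mg/kg or stopping

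*Combined protocol and SAP*

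**What the plan says.** Subjects start at 10 mg/kg on days 1 and 8 of a 21-day cycle. Four parts of Section 6.4.1 bear on what follows a severe neutropenia.

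- **The paragraph just before Table 7** covers grade 3 or higher neutropenia on a scheduled treatment day in a subject already on growth-factor prophylaxis, recovering to grade 2 or lower in 2 or 3 weeks. The first event gives 7.5 mg/kg. The step to 5 mg/kg is "for the second event that occurs while the patient is receiving prophylactic growth factors". The third occurrence on growth factor ends treatment.
- **Table 7 and the text below it** give one first/second/third ladder (7.5 mg/kg, 5 mg/kg, discontinue) for a list of toxicities joined by OR. The list includes Grade 3 febrile neutropenia, Grade 3 gastrointestinal toxicity, and Grade 3 hematologic toxicity at a scheduled treatment that delays the dose 2 or 3 weeks. There is no growth-factor condition, and the text below makes the reduction permanent and mandatory.
- **The general Grade 3 paragraph** says that when recovery "delays the next dose by 2 or 3 weeks, treatment must be resumed at a reduced dose (Table 7"). It recommends later G-CSF "to prevent recurrence of neutropenia that would require a dose reduction".
- **The neutropenia paragraph that follows it** tells sites to "hold day 8, initiate growth factor support and administer prophylactic growth factors with each subsequent cycle". It then says "Resume dosing at the next cycle if toxicity recovers to" grade 2 or lower within three weeks, and names no dose.

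On who is likely to be on growth factor, Section 6.4 says "Growth factors are required at cycle 1 for all patients" aged 65 or over, directs early use in patients at high risk of neutropenia, and adds "Growth factors should be initiated once the ANC starts decreasing and may be used prophylactically as clinically indicated". For a Cycle 1 Day 1 ANC from 1000 to below 1500, Section 6.4.1 adds "It is recommended that growth factor support prophylaxis be administered to subjects who receive treatment". Dose re-escalation is not allowed.

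**The concern.** A Grade 3 neutropenia on growth factor that delays a dose by 2 or 3 weeks meets both rules. If the subject has already had a Table 7 event that the growth-factor paragraph does not count, the new event is the first under one rule and the second under the other. No sentence in 6.4 or 6.4.1 says that the counts are shared or which one governs.

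What is at stake is dosing safety and consistency between sites. Under the growth-factor count, a subject already at 7.5 mg/kg stays at 7.5 mg/kg after a further severe toxicity for which Table 7 requires a reduction. Under Table 7 the subject goes to 5 mg/kg and, because re-escalation is barred, stays there.

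**Working it through.** **Reproducing the ladder.** From a 10 mg/kg start: 10 × 0.75 = 7.5 mg/kg and 10 × 0.50 = 5 mg/kg, then stop. Both rules state these figures; they differ only in what is counted.

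**Notation.** G is a Grade 3 neutropenia on a scheduled day, on growth factor, with a 2-3 week delay; it counts under both rules. T is a Table 7 event that the growth-factor paragraph does not count. Where only Table 7 applies, it supplies the dose.

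**All events on growth factor (G, G, G).** Both rules give 7.5, 5, stop. There is no conflict.

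**One outside event first (T, G, G, G).**

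| Event | Table 7 count | Growth-factor count |
|---|---|---|
| 1 (T) | 7.5 mg/kg | does not apply; Table 7 gives 7.5 mg/kg |
| 2 (G) | 5 mg/kg | 7.5 mg/kg |
| 3 (G) | stop | 5 mg/kg |
| 4 (G) | already stopped | stop |

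**Outside event second (G, T, G).** Both stand at 7.5 mg/kg after event 1, and Table 7 takes the subject to 5 mg/kg at event 2. At event 3 Table 7 says stop, while the growth-factor paragraph sees its second event and says 5 mg/kg.

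**Size of the gap in T, G, G, G**, with two infusions per cycle:
- After event 2: 2 × 7.5 = 15 v 2 × 5 = 10 mg/kg per cycle, a difference of (15 − 10)/15 = 33%. For the 70-kg subject in the protocol's preparation example: 70 × 7.5 = 525 v 70 × 5 = 350 mg per infusion, or 1050 v 700 mg per cycle.
- After event 3: 2 × 5 = 10 v 0 mg/kg per cycle, or 700 v 0 mg at 70 kg.

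**What can be the outside event T?**
- Febrile neutropenia. Table 7 ties it neither to a scheduled day nor to growth factor. An episode between doses is outside the growth-factor count even in a subject aged 65 or over on mandatory prophylaxis.
- Neutropenia off growth factor with a 2-3 week delay. This arises mainly in subjects under 65 without early prophylaxis.
- Grade 3 gastrointestinal toxicity, if Table 7 pools toxicity types. The single ladder over an OR-joined list favours pooling.

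**Neutropenia off growth factor at event 1.** The neutropenia paragraph restarts dosing with growth factor and states no reduction, so it can be read as 10 mg/kg. Table 7 gives 7.5 mg/kg. On that reading the rules already differ at event 1: 2 × 10 = 20 v 2 × 7.5 = 15 mg/kg per cycle. The general paragraph's remark about neutropenia requiring a dose reduction points towards Table 7 but does not settle the matter.

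**The case against.** The strongest reply is that Table 7 plainly governs. The overlapping event is on its list, the reduction is mandatory, and the general Grade 3 paragraph sends 2-3 week delays to the same table. The growth-factor paragraph, with an identical ladder, would then be only an instance of it. Part of this stands: a reader might infer that two sites could dose differently with both fully compliant, and the documents do not support that. A site that stays at 7.5 mg/kg at event 2 departs from Table 7's mandatory text. But the reply leaves the growth-factor qualifier in the second and third steps with no function, and a site that lets the more specific rule govern has wording to point to. The conflict is real even though the two readings are not equally strong.

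A second reply is that the diarrhea route fails if Table 7 counts per toxicity type, or if its 48-hour persistence condition also limits gastrointestinal events. That stands as a limit on that route. It does not affect routes that begin with febrile neutropenia or neutropenia off growth factor.

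Third, Section 6.4 wants reductions avoided through active management, so exempting neutropenia off growth factor may be closer to the intent. That is a fair clinical argument about which rule to choose, but the choice still has to be written down.

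**Conclusion.** The point holds as a minor conflict between two stated dosing rules. It needs one earlier Table 7 event outside the growth-factor count, then at least one Grade 3 neutropenia delay on growth factor for a dose difference (7.5 v 5 mg/kg) in the T-first sequence, and two for a stopping difference. If the outside event comes second, the stopping difference appears at the third event. All of this assumes a 10 mg/kg start.

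Three stronger readings are not supported:
- A reader might infer that the rules always agree at the first event. For neutropenia off growth factor that is only one reading.
- A reader might scale the rates in Table 3 to the 55 planned subjects: febrile neutropenia of grade 3 or higher, 18/420 × 55 = 2.4, and diarrhea, 37/420 × 55 = 4.8. These are all-cause rates over all doses, whereas Table 7 needs treatment-related events, and they describe at most a first step. The documents give no rate of 2-3 week neutropenia delays and none by growth-factor use, so the number affected cannot be derived. It is probably small.
- A reader might infer an effect on PSA response or 6-month rPFS. Nothing in the documents shows one.

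**What to change.** In the next amendment:

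1. Add a governing sentence to 6.4.1 and a note to Table 7: all qualifying events, on or off growth factor, count on the single Table 7 ladder (first 7.5 mg/kg, second 5 mg/kg, third stop), so a subject already reduced under Table 7 moves to the next lower level.
2. Keep the paragraph before Table 7 but delete its separate count of events on growth factor.
3. Change Table 7's delay trigger from Grade 3 to grade 3 or higher hematologic toxicity. Otherwise a Grade 4 neutropenia lasting under 7 days with a 2-3 week delay, which that paragraph now covers, would have no matching entry.

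If the clinical team prefers to exempt neutropenia off growth factor, Table 7 and the general Grade 3 paragraph must state the exemption and the resumption dose, and say whether a non-neutropenia event advances the neutropenia count.

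The cost is text edits only, with no extra patients, procedures or data. The downside of the single ladder is that some subjects reduce or stop one event earlier than under the growth-factor-only count.
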